## SPONSOR: GW PHARMA LIMITED

## 5.3.5 Post-trial Provision

There will be no post-trial provision of nabiximols.

A summary of the results of this trial will be made available on https://www.clinicaltrials.gov as required by US law and on https://www.clinicaltrialsregister.eu/ of the European Union (EU) Clinical Trials Register.

#### SPONSOR: GW PHARMA LIMITED

# 6 PATIENT ELIGIBILITY

Investigators are responsible for confirming patient eligibility and will be required to maintain a log that includes limited information about all screened patients (initials, age, race, and sex; as allowed per local regulations) and outcome of screening.

# 6.1 Inclusion Criteria

#### Screening (Visit 1)

For inclusion in the trial, patient must fulfill ALL of the following criteria:

- 1. Male or female aged 18 years or above.
- 2. Willing and able to give informed consent for participation in the trial (see Section 15.2).
- 3. Willing and able (in the investigator's opinion) to comply with all trial requirements. (With the exception of the T25FW test, if the patient is non-ambulatory).
- 4. Has had a diagnosis with any disease subtype of MS, by revised 2017 McDonald criteria, for at least 12 months prior to Visit 1 and is expected to remain stable for the duration of the trial.
- 5. Has had treatment with at least 1 optimized oral antispasticity therapy prior to Visit 1 that must include either oral baclofen or oral tizanidine (monotherapy or combination therapy).
- 6. Currently receiving optimized treatment with at least 1 oral antispasticity medication (baclofen, tizanidine, or dantrolene) and has been stable for at least 30 days prior to Visit 1. Despite optimization, the patient does not have adequate relief of spasticity signs and symptoms, including muscle spasms. Optimization of antispasticity medications is defined as having reached the most efficacious and best tolerated dose according to the relevant local prescribing information. The patient must be willing to maintain the same antispasticity medication and not plan to initiate a new course of physiotherapy for the duration of the trial.
- 7. If currently receiving an MS disease-modifying therapy, it must be at a stable dose for at least 3 months prior to Visit 1 and is expected to remain stable for the duration of the trial.
- 8. If currently receiving dalfampridine or fampridine, it must be at a stable dose for at least 3 months prior to Visit 1 and is expected to remain stable for the duration of the trial.
- 9. Willing to allow the responsible authorities to be notified of participation in the trial, if mandated by local law.
- 10. Willing to allow his or her primary care practitioner (if he or she has one) and/or treating neurologist (if he or she has one) to be notified of participation in the trial, if the primary care practitioner/treating neurologist is different than the investigator.

Additional Inclusion Criteria at Randomization (Visit 2)

Patients are eligible for randomization in the trial if, in addition to continuing to meet the Screening (Visit 1) inclusion criteria, they also meet ALL of the following criteria during the first 28 days of the baseline period. (Note: patients are expected to start completing their electronic diary in the evening of their screening visit):

- 11. In the opinion of the investigator, the patient is able to interpret and report spasm count data accurately
- 12. Completed their electronic diary for at least 25 of the first 28 days of the baseline period
- 13. Has an average daily spasm count of  $\geq$  4 during the first 28 days of the baseline period, as recorded by the patient
- 14. Has no more than 35 spasms on any single day of the first 28 days of the baseline period, as recorded by the patient
- 15. Does not have > 7 consecutive days without experiencing any spasm during the first 28 days of the baseline period

If, for any reason, the patient is unable to attend the site for randomization within the visit window, the site should contact the Medical Monitor or the sponsor to discuss.

In addition to meeting the Screening (Visit 1) inclusion criteria and additional inclusion criteria 11 to 14, any patient with more than 28 days between Visit 1 and Visit 2 would need to meet ALL of the following criteria prior to randomization:

- 16. Completed their electronic diary for at least 85% of days between Visit 1 and Visit 2
- 17. Has an average daily spasm count of  $\geq$  4 between Visit 1 and Visit 2 (randomization), as recorded by the patient
- 18. Has no more than 35 spasms on any single day between Visit 1 and Visit 2, as recorded by the patient
- 19. Does not have > 7 consecutive days without experiencing any spasm between Visit 1 and Visit 2

# 6.2 Exclusion Criteria

The patient may not enter the trial if ANY of the following apply:

- 1. Previously participated in a clinical trial of nabiximols or has had a poor previous response or intolerance to nabiximols or other cannabinoid-containing products used for therapeutic purposes.
- 2. Any concomitant disease or disorder that has spasticity-like symptoms or that may influence the patient's level of spasticity.
- 3. Medical history suggests that relapse/remission is likely to occur during the trial, which, in the opinion of the investigator, is expected to influence the patient's spasticity.

- 4. Has had a relapse of MS within the 60 days prior to Visit 1.
- 5. Has taken cannabis, or a cannabis-derived product for medicinal or recreational use within the 30 days prior to screening (Visit 1) or a positive blood drug test for THC at screening (Visit 1).
- 6. Is unwilling to abstain from use of cannabis, or a cannabis-derived product for medicinal or recreational purposes for the duration of the trial.
- 7. Currently using botulinum toxin injection for the relief of spasticity (within 6 months of Visit 1)
- 8. Is unwilling to abstain from the use of botulinum toxin injection for the relief of spasticity for the duration of the trial.
- 9. Currently taking antipsychotic medication.
- 10. Currently taking benzodiazepines, unless doses and dosing regimen have been stable for at least 30 days prior to Visit 1.
- 11. Has any known or suspected hypersensitivity to cannabinoids or any of the excipients of the IMP.
- 12. Has experienced myocardial infarction or clinically significant cardiac dysfunction within the 12 months prior to Visit 1 or has a cardiac disorder that, in the opinion of the investigator, would put the patient at risk of a clinically significant arrhythmia or myocardial infarction.
- 13. Has a diastolic blood pressure of < 50 mmHg or > 105 mmHg or systolic blood pressure < 90 mmHg or > 150 mmHg (when measured in a supine position at rest for 5 minutes), or a postural drop in the systolic blood pressure of  $\geq$  20 mmHg or in diastolic blood pressure of  $\geq$  10 mmHg at Visit 1. All measurements will be performed singly and can be repeated once, if any are outside the reference range but not considered clinically significant.
- 14. Has clinically significant impaired renal function at Visit 1, as evidenced by an estimated creatinine clearance lower than 50 mL/min. All measurements will be performed singly and can be repeated once, if any are outside the reference range but not considered clinically significant.
- 15. Has moderately impaired hepatic function at Visit 1, defined as serum alanine aminotransferase (ALT) or aspartate aminotransferase (AST)  $\ge 2 \times$  upper limit of normal (ULN). All measurements will be performed singly and can be repeated once, if any are outside the reference range but not considered clinically significant.
- 16. Male and fertile (i.e., after puberty unless permanently sterile by bilateral orchiectomy) unless willing to ensure that he uses male contraception (condom or vasectomy) or remains sexually abstinent during the trial and for 3 months thereafter.
- 17. Female and of childbearing potential (i.e., following menarche and until becoming postmenopausal for  $\geq$  12 consecutive months with a follicle stimulating hormone (FSH)  $\geq$  30 mIU/mL unless permanently sterile by hysterectomy, bilateral salpingectomy, or bilateral oophorectomy) unless willing to ensure that she uses a highly effective method of birth control (e.g., intrauterine device/hormone-releasing system, bilateral tubal occlusion, vasectomized partner, other highly effective hormonal methods or sexual

abstinence) during the trial and for 3 months thereafter. Patients using combined hormonal methods or a progestogen-only pill or injection or implant should use an additional barrier method such as a condom or diaphragm during the trial and for 3 months thereafter (see Section 9.2.2).

- 18. Female and pregnant (positive pregnancy test at Visit 1 or Visit 2 [predose]), lactating, or planning pregnancy during the course of the trial or within 3 months thereafter.
- 19. Received an IMP within the 30 days prior to Visit 1.
- 20. Has any other clinically significant disease or disorder (including seizure disorder) that, in the opinion of the investigator, may put the patient, other patients, or site staff at risk because of participation in the trial, influence the interpretation of trial results, or may affect the patient's ability to take part in the trial.
- 21. Has any abnormalities identified following a physical examination, clinical laboratory, serology, or other applicable screen procedures that, in the opinion of the investigator, would jeopardize the safety of the patient or the conduct of the study if he or she took part in the trial.
- 22. Has any history of suicidal behavior in the 5 years prior to Visit 1 or a suicidal ideation score of 3, 4, or 5 on the Columbia Suicide Severity Rating Scale (C-SSRS) in the month prior to Visit 1.
- 23. Has a history of severe psychiatric disorder that may be exacerbated by the use of a cannabinoid-containing product.
- 24. Has donated blood during the 3 months prior to Visit 1 and is unwilling to abstain from donation of blood during the trial.
- 25. Has been previously randomized into this trial.
- 26. Has any known or suspected history of alcohol or substance use disorder within 1 year prior to Visit 1. Patients with nicotine use disorder are allowed to enroll.
- 27. Currently using an illicit drug or current nonprescribed use of any prescription drug. A positive drug test at Visits 1 or 2 for a prescribed medication is not exclusionary at the investigator's discretion. A positive drug test at Visit 1 or predose at Visit 2 for illicit drugs may be repeated locally at the investigator's discretion.
- 28. Has any planned clinical interventions or intends to change any or all medications that may have an effect on spasticity or MS during the trial.
- 29. Currently taking drugs that are solely metabolized by UGT1A9 and UGT2B7 (see APPENDIX 4).
- 30. Currently taking strong CYP3A4 inducers (e.g., rifampicin, carbamazepine, phenytoin, phenobarbital, St John's Wort).
- 31. There is an expectation that the participant will require a new course of treatment with strong CYP3A4 inhibitors during the study duration (e.g., participant with recurrent fungal infections requiring intermittent treatment with itraconazole).

32. Patients who receive a positive coronavirus disease 2019 (COVID-19) antigen test result, potentially suggesting infective status, before randomization may be screen failed, at the discretion of the investigator.

Individuals who do not meet the criteria for participation in this trial (screen failure) because of, for example, fever due to a brief acute upper respiratory illness, having taken a prohibited over the counter medication within the excluded period, recent blood donation, due to the inclusion criterion related to the ability to interpret and report spasm count data accurately, or who could not be randomized for logistical reasons, can be rescreened once, at the discretion of the investigator or designee with sponsor approval. Rescreened participants should be assigned a new screening number.

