	abstinent during the trial and for 3 months thereafter
	6

•	Female and of childbearing potential (i.e., following menarche
	and until becoming postmenopausal for $\geq 12$ consecutive
	months with a follicle stimulating hormone (FSH)
	$\geq$ 30 mIU/mL unless permanently sterile by hysterectomy,
	bilateral salpingectomy, or bilateral oophorectomy) unless
	willing to ensure that she uses a highly effective method of
	birth control (e.g., intrauterine device/hormone-releasing
	system, bilateral tubal occlusion, vasectomized partner, other
	highly effective hormonal methods or sexual abstinence)
	during the trial and for 3 months thereafter. Patients using
	combined hormonal methods or a progestogen-only pill or
	injection or implant should use an additional barrier method
	such as a condom or diaphragm during the trial and for
	3 months thereafter
•	Female and pregnant (positive pregnancy test at Visit 1 or
	Visit 2 [predose]), lactating, or planning pregnancy during the
	course of the trial or within 3 months thereafter
•	Received an IMP within the 30 days prior to Visit 1
•	Has any other clinically significant disease or disorder
	(including seizure disorder) that, in the opinion of the
	investigator, may put the patient, other patients, or site staff at
	risk because of participation in the trial, influence the
	interpretation of trial results, or may affect the patient's ability
	to take part in the trial
•	Has any abnormalities identified following a physical
	examination, clinical laboratory, serology, or other applicable
	screen procedures that, in the opinion of the investigator,
	would jeopardize the safety of the patient or the conduct of the
	study if he or she took part in the trial
•	Has any history of suicidal behavior in the 5 years prior to
	Visit 1 or a suicidal ideation score of 3, 4, or 5 on the C-SSRS
	in the month prior to Visit 1
•	Has a history of severe psychiatric disorder that may be
	exacerbated by the use of a cannabinoid-containing product
•	Has donated blood during the 3 months prior to Visit 1 and is
	unwilling to abstain from donation of blood during the trial
•	Has been previously randomized into this trial

• Has any known or suspected history of alcohol or substance
use disorder within 1 year prior to Visit 1. Patients with
nicotine use disorder are allowed to enroll
• Currently using an illicit drug or current nonprescribed use of
any prescription drug. A positive drug test at Visits 1 or 2 for a

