# 9.1.2 Visit 2 (Day 1, Randomization)

Following the 28-day baseline period, patients will attend the site for Visit 2 on Day 29, a visit window of +2 days is permitted but it is preferred that the visit is performed on the scheduled visit day, where possible. If, for any reason, the patient is unable to attend the site for randomization within the visit window, the site should contact the Medical Monitor or the sponsor to discuss; please note the eligibility criteria the patient needs to meet should this occur.

The following assessments/procedures will be performed:

- Eligibility check
- Randomization (Section 7.2)
- Concomitant medications review
- AE review
- Physical and oral mucosa examinations
- Body weight measurement
- Vital signs measurement

- 12-lead ECG
- Clinical laboratory blood sampling (hematology and biochemistry)
- Urine drug screen (including THC)
- Urine pregnancy test (if appropriate)
- PK blood sampling (Section 9.2.12.1)
- MSSS-88 assessment (Section 9.2.15.2)
- C-SSRS assessment
- T25FW test (Section 9.2.15.4)
- SF-36 assessment (Section 9.2.15.6)
- IMP dosing training and dispensing (Section 9.2.14.4)

Following predose assessments and after IMP dosing training and IMP dispensing, site staff will provide patients with an example titration schedule and instructions to record IMP dosing information in the patient electronic diary. Patients will take the first dose of IMP on the evening of Visit 2 (Day 1).

See Section 8.1.1 and Section 8.1.2 for IMP dosing and administration information.

Patients should be reminded to record their spasm count, 11-point NRS spasm severity score, 11-point NRS spasticity score, and use of antispasticity medications in the electronic diary once daily, around the same time of the day, preferably in the evening before retiring to sleep. In addition, on the day before Visits 3, 4, and 5 patients will be prompted to record whether they started their morning and evening doses of IMP within 30 minutes of a meal.

Each site will have the option to follow up with the patient through telephone calls during the titration phase to monitor the patient's titration, safety and tolerance, and electronic daily diary reporting.

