# 9.2.15.2 Columbia-Suicide Severity Rating Scale

The definitions of behavioral suicidal events used in this scale are based on those used in the Columbia Suicide History Form. Questions are asked on suicidal behavior, suicidal ideation, and intensity of ideation. At Screening (Visit 1), questions will be in relation to lifetime experiences (baseline). Questioning at all subsequent visits will be in relation to the last assessment (since last visit).

The C-SSRS is to be administered by the investigator or his/her qualified designee at Visits 1 through 6 as indicated in the schedule of assessments (see APPENDIX 1); "qualified designee" is defined as anyone who has completed the C-SSRS training within the past 2 years or has continually administered C-SSRS assessments throughout the trial since obtaining the training certificate. The survey should be completed by the same assessor, where possible, throughout the trial. Assessments will be conducted only if patients are capable of understanding and answering the questions, in the investigator's opinion.

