#### SPONSOR: GW PHARMA LIMITED

# 10 WITHDRAWAL

In accordance with the Declaration of Helsinki, the ICH Harmonised Guideline: Integrated Addendum to ICH E6(R1): Guideline for GCP E6(R2), the US FDA regulations relating to GCP and clinical trials, the EU Clinical Trials Directive, the EU GCP Directive, and/or other applicable regulations, a patient has the right to withdraw from the trial at any time and for any reason, with no obligation to provide a reason, and without prejudice to his or her future medical care by the physician or at the institution.

The patient must be withdrawn from the trial if any of the following apply:

- Administrative decision by the investigator, GW, or a regulatory authority
- Withdrawal of patient consent
- Lost to follow-up

The patient must cease IMP and should remain in the trial if any of the following apply:

- Pregnancy
- Protocol deviation that is considered to potentially compromise the safety of the patient
- Suicidal behavior, or suicidal ideation score of 4 or 5 during the treatment period, as evaluated with the C-SSRS
- ALT or AST  $> 3 \times$  ULN with the appearance of fatigue, nausea, vomiting, right upper quadrant pain or tenderness, fever, rash, and/or eosinophilia (> 5%)
- ALT or AST  $> 5 \times ULN$
- ALT or AST > 3 × ULN and (total bilirubin [TBL] > 2 × ULN or international normalized ratio [INR] > 1.5)
- Any prohibited medication after Visit 1

The patient may be required to cease IMP at the discretion of the investigator and should remain in the trial for any of the following reasons:

- Did not meet eligibility criteria
- Patient noncompliance
- AE (including clinically significant laboratory result) that, in the opinion of the investigator, would compromise the continued safe participation of the patient in the trial
- Any evidence of drug abuse or diversion

- Disease progression (defined as a relapse of MS requiring a change in treatment)
- A positive COVID-19 test result after randomization

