#### SPONSOR: GW PHARMA LIMITED

	Screening		Safety Follow-up Period				
Visit	1	2	3	4	5	6	7
Day Number (Visit Window)	Days -28	Day 1/Randomizati on  (+2)	Day 15 14 days from Day 1 (± 3 days)	Day 29 28 days from Day 1 (± 3 days)	Day 57 56 days from Day 1 (± 7 days)	End of Treatment /Early Withdrawal Day 85 84 days from Day 1 (± 7 days)	Day 99 14 days from Visit 6 (± 4 days)
Spasm count training	Х	X	Х	Х	Х	X	X
T25FW		X				Х	
IMP dosing training		X					
IMP collection and compliance review			Х	Х	Х	Х	
IMP dispensing 		X	Х	Х	Х		

C-SSRS = Columbia-Suicide Severity Rating Scale; COVID-19 = coronavirus disease 2019; ECG = 12-lead electrocardiogram; FSH = follicle stimulating hormone; IMP = investigational medicinal product; MSSS-88 = Multiple Sclerosis Spasticity Scale; MUS = Medication Use Survey; NRS = Numerical

Rating Scale; PK = pharmacokinetics; SF-36 = 36-Item Short Form Health Survey; T25FW = Timed 25-Foot Walk; THC =  $\Delta^9$ -tetrahydrocannabinol.

 Visit 2 will occur 28 days after Visit 1. A visit window of +2 days is permitted but it is preferred that the visit is performed on the scheduled visit day, where possible.

 A comprehensive physical examination, including an assessment of height, will be completed at Screening (Visit 1) only, subsequent physical examinations will be symptom-directed.

 A positive urine drug screen at Visit 1 or pre dose at Visit 2 for illicit drugs may be repeated locally at the investigator's discretion. Urine drug tests must not be performed once the patient has received IMP

Confidential

Clinical Protocol Template (Phase 2–4)

Page 102 of 106

Study Code: GWSP18023	
EudraCT Number: 2019-002623-14	
Protocol V5 01Jun2021	

5

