#### SPONSOR: GW PHARMA LIMITED

Serum pregnancy test at Visits 1 and 6; urine pregnancy test before randomization at Visit 2. Note that pregnancy testing is not required for females postmenopausal for  $\geq$  12 consecutive months with a FSH  $\geq$  30 mIU/mL.

On the day before PK blood sampling, patients will be prompted to record whether they started their morning and evening doses of IMP within 30 minutes of a meal. During the visits, the exact time of PK blood sampling and the time of the patient's snacks and meals should be recorded. There will be 2 options for the collections of PK samples:

**Option 1**: For patients choosing the sparse PK sampling option, blood samples will be taken as follows: Visit 2 - 1 sample predose; Visits 3, 4, 5, and 6 - 1 sample collected at any time during the visit. **Option 2**: For patients choosing the semi-intensive PK sampling option, blood samples will be taken as follows: Visit 2 - 1 sample predose; At 1 visit (either Visit 3, 4, or 5), -1 sample predose (i.e., prior to administration of IMP at the investigational site), 1 sample between 2 and 3 hours postdose, 1 sample between 4 and 6 hours postdose, and 1 sample between 6 and 8 hours postdose. There must be a minimum period of at least 2 hours between each of the 4 blood-sampling time-points. The predose sample will be taken prior to the morning IMP dose. On the day of the semi-intensive PK sampling, the patient must bring their study medication with them to the visit and not take their morning IMP dose until instructed to do so by the site staff.

 Patients will record their spasm count, 11-point NRS spasm severity score, 11-point NRS spasticity score, and use of antispasticity medications in an electronic diary once daily, around the same time of day, preferably in the evening before retiring to sleep, during the baseline period prior to Visit 2 and throughout the trial until Visit 7. Patients are to be instructed to start completing their electronic diary in the evening of their screening visit. IMP dosing will be recorded by the patient in the electronic diary from Visits 2 through 6.

 Data for the day of Visit 7 should not be entered in the electronic diary. Site staff will confirm that data that relates to the day prior to attending the site for Visit 7 has been entered in the electronic diary prior to completion of the trial.

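### No explicit mandatory criterion bars randomization on a positive Visit 2 C-SSRS: exclusion 22 stops at Visit 1, and ideation score 3 is also outside the mandatory Section 10 stop

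*Protocol*

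**What the plan says.** Exclusion 22 in Protocol Section 6.2 is the only eligibility criterion that names the C-SSRS: "Has any history of suicidal behavior in the 5 years prior to Visit 1 or a suicidal ideation score of 3, 4, or 5". The ideation limb covers the month before Visit 1. The synopsis carries the same criterion, beginning "Has any history of suicidal behavior in the 5 years prior to" Visit 1.

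Section 9.1.2 lists "C-SSRS assessment" among the Visit 2 procedures, together with an eligibility check and randomization. Section 9.2.15.2 fixes the recall period after screening: "Questioning at all subsequent visits will be in relation to the last assessment (since last visit"). Appendix 1, footnote 8, confirms that the since-last-visit version is used from Visit 2 onward.

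Section 10 makes the following a reason for compulsory cessation of IMP, with the patient staying in the trial: "Suicidal behavior, or suicidal ideation score of 4 or 5 during the treatment period, as evaluated with the C-SSRS".

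Pregnancy is handled differently. Exclusion 18 begins "Female and pregnant (positive pregnancy test at Visit 1 or Visit 2 [predose"], and Appendix 1, footnote 4, places the "urine pregnancy test before randomization at Visit 2".

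**The concern.** The Visit 2 C-SSRS asks about the interval that exclusion 22 does not reach. Checking exclusion 22 again at Visit 2 does not help, because its look-back windows still end at Visit 1. Followed as written, the protocol lets a patient who reports new suicidal behavior, or ideation of 3 or more, during the baseline period be randomized on the day of first dosing unless the investigator invokes a discretionary exclusion. The same result a month earlier would have excluded the patient automatically.

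The main stakes are patient safety and consistent handling across sites. The protocol treats this as a real risk area: exclusion 23 concerns psychiatric disorder that cannabinoids could worsen, Section 9.2.18.1.1 lists suicidal thoughts as a triggering event, and Section 14 states that there is no data safety monitoring committee.

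Safety reporting is affected too. SAP Section 10.4.2 takes only the Visit 2 C-SSRS as baseline, and SAP Section 10.25 counts treatment-emergent serious ideation only from a baseline of 0 to 3. A patient randomized with a Visit 2 score of 4 or 5 could not be counted as such a case. Suicidal behavior reported at baseline likewise removes the patient from the count of emergent behavior.

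**Working it through.** This is a comparison of texts; the plan states no figure to reproduce.

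**Step 1. What is re-applied at randomization.** Section 6.1 requires that the Visit 1 inclusion criteria still hold and adds criteria 11 to 15. Criteria 16 to 19 are added if more than 28 days have passed. These additions concern the diary and spasm data, including the investigator's view of reporting accuracy. None concerns the C-SSRS. The sponsor therefore did write rules for a prolonged Visit 1 to Visit 2 interval, but not for suicidality.

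**Step 2. The length of the interval.** Appendix 1, footnote 1: "Visit 2 will occur 28 days after Visit 1. A visit window of +2 days is permitted". The Visit 2 C-SSRS thus covers 28 to 28 + 2 = 30 days. Sections 6.1 and 9.1.2 allow a longer delay after discussion with the Medical Monitor or sponsor and give no upper limit.

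**Step 3. Each result against each rule.**

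| C-SSRS result | Automatic exclusion when in the Visit 1 window | Explicit mandatory bar at Visit 2 | Mandatory Section 10 IMP stop, if Visit 2 counts as treatment period |
|---|---|---|---|
| Suicidal behavior | Yes | No | Yes |
| Ideation 5 | Yes | No | Yes |
| Ideation 4 | Yes | No | Yes |
| Ideation 3 | Yes | No | No |
| Total | 4 of 4 | 0 of 4 | 3 of 4 |

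One of the four, score 3, meets neither mandatory rule at Visit 2.

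**Step 4. Whether Section 10 applies on Day 1.** The definition of terms ends the baseline period on the day before randomization, and Appendix 1 appears to place Visit 2 among the treatment-period columns, so this reading is defensible. It is not certain. Even if accepted, the rule stops IMP in a patient who is already randomized, should stay in the trial and, if later withdrawn, is not replaced (Section 7.2).

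**Step 5. Order of procedures at Visit 2.** Section 9.1.2 lists randomization second and the C-SSRS well below it. Its reference to predose assessments supports doing the C-SSRS before the first spray, but not before the randomization call. For the urine pregnancy test, the order relative to randomization is stated.

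**The case against.** The strongest reply is that real safeguards exist. Exclusions 20 and 21 carry no Visit 1 date, and the opening of Section 6.2 is mandatory once either is judged to apply. Visit 2 has an eligibility check, and the C-SSRS is administered by the investigator or a trained designee, so the result can be known on site that day. The first dose is taken on the evening of Visit 2; if the Section 10 stop applies then, a patient with behavior or a score of 4 or 5 need never be dosed. Section 10 also lets the investigator stop IMP for a safety-relevant adverse event, which could include new ideation at score 3. Fixed limits tied to Visit 1 are common in this protocol: blood pressure, renal and hepatic limits follow the same pattern although vital signs and biochemistry are repeated at Visit 2. The threshold at Visit 2 is a medical choice, since the sponsor set 3 to 5 for entry and 4 to 5 for compulsory stopping. Finally, the SAP addendum records that enrollment was halted on 9 November 2022.

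Much of this stands as mitigation. Drug exposure is not inevitable, score 3 is outside only the mandatory part of Section 10, and an amendment can no longer change who enters this trial. None of it supplies the missing rule. Exclusions 20 and 21 and the adverse-event stop rest on investigator opinion and do not name the C-SSRS. The Section 10 stop acts after randomization. The Visit 1 limits for blood pressure and laboratory values show the same pattern elsewhere; they do not justify it for suicidality.

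**Conclusion.** The concern holds. No explicit mandatory criterion uses the Visit 2 C-SSRS to bar randomization: 0 of the 4 results that exclude automatically at Visit 1 do so at Visit 2. Three of 4 are arguably caught by the Section 10 stop after randomization, and score 3 by no mandatory rule. The interval is assessed, by the Visit 2 C-SSRS and adverse event review; what is missing is a decision rule.

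These are counts of result categories, not estimates of risk. The documents do not show how many patients would have a new positive result between visits, and differing handling across about 65 sites is a possibility, not an observation. The 3 of 4 figure assumes that Visit 2 belongs to the treatment period. The change should be made because it applies the sponsor's own entry threshold to an assessment already performed. With enrollment halted, its practical use is mainly in a successor protocol.

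**What to change.** - **Exclusion 22 and its synopsis copy:** add that any suicidal behavior, or an ideation score of 3, 4 or 5, between Visit 1 and randomization, as recorded on the Visit 2 C-SSRS, also excludes the patient. The sponsor's physicians may confirm the threshold.
- **Section 9.1.2:** require the Visit 2 C-SSRS to be completed and reviewed before the IRT randomization call, giving it the same place in the sequence as the urine pregnancy test.

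The cost is one clause in two places and one sentence. No assessment is added. The downside is an occasional extra screen failure.
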